2 PROTOCOL SYNOPSIS

Title A Phase 3, Open-label, Rollover Study to Evaluate the Safety and Efficacy of Long-term Treatment With Tezacaftor in Combination With Ivacaftor in Subjects With Cystic Fibrosis Aged 6 Years and Older, Homozygous or Heterozygous for the *F508del-CFTR* Mutation

Brief Title A Study to Evaluate the Safety and Efficacy of Long-term Treatment With TEZ/IVA in CF Subjects With an *F508del-CFTR* Mutation

Clinical Phase and Clinical Study Type Phase 3, safety and efficacy

Objectives Primary Objective

To evaluate the long-term safety and tolerability of tezacaftor in combination with ivacaftor (TEZ/IVA) in subjects with cystic fibrosis (CF) aged 6 years and older, homozygous or heterozygous for the *F508del* mutation

Secondary Objective

[figure not shown]
To evaluate the long-term efficacy of TEZ/IVA in subjects with CF aged 6 years and older, homozygous or heterozygous for the *F508del* mutation

[figure not shown]
Endpoints Primary Endpoint

Safety and tolerability of long-term TEZ/IVA treatment based on adverse events (AEs), clinical laboratory values (serum chemistry, hematology, lipids, and vitamins), standard 12-lead ECGs, physical examinations (PEs), vital signs, ophthalmologic examinations, and pulse oximetry

Secondary Endpoints

- Absolute change from baseline in lung clearance index_{2.5} (LCI_{2.5}; for subjects from Study VX16-661-115 [Study 115] and the Study VX15-661-113 Part B [Study 113B] LCI Substudy only)
- Absolute change from baseline in sweat chloride
- Absolute change from baseline in Cystic Fibrosis Questionnaire–Revised (CFQ-R) respiratory domain score
- Absolute change from baseline in body mass index (BMI)

Number of Subjects Study VX17-661-116 is a rollover study. Approximately 56 subjects from Study 113B and 65 subjects from Study 115 are potentially eligible for enrollment. Up to approximately 121 subjects are potentially eligible for enrollment.

Study Population Male and female subjects with CF aged 6 years and older, who completed Study 113 B or Study 115 and are

- homozygous for *F508del* (F/F),
- heterozygous for *F508del* and a second allele with a residual CFTR-function mutation (F/RF), or
- heterozygous for *F508del* and a second allele that has been shown to be responsive to TEZ/IVA

Investigational Drug **Active substance:** TEZ and IVA
Activity: CFTR corrector and potentiator (increased Cl⁻ secretion)

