12 STATISTICAL AND ANALYTICAL PLANS

12.1 Sample Size and Power

This open-label rollover study will enroll subjects from Study 113B and Study 115. No formal sample size calculations have been performed. Approximately 56 subjects from Study 113B and approximately 65 subjects from Study 115 are potentially eligible for enrollment.

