12.3.4.1 Adverse Events

AEs will be classified as pretreatment AEs or treatment-emergent AEs (TEAEs), defined as follows:

Pretreatment AE: any AE that started before the first dose of study drug

TEAE: any AE that worsened (either in severity or seriousness) or that was newly developed at or after the first dose date of study drug through the end of the TE period.

For AEs with completely missing or partially missing start dates, if there is no clear evidence that the AEs started before or after study treatment, the AEs will be classified as TEAEs.

Details for imputing missing or partial start dates of AEs are described in the SAP.

AE summary tables will be presented for TEAEs only, overall and by treatment group, and will include the following:

- All TEAEs
- TEAEs by strongest relationship
- TEAEs by maximum severity
- TEAEs leading to treatment discontinuation
- Serious TEAEs
- TEAEs leading to death

Summaries will be presented by MedDRA SOC and PT using frequency counts and percentages (i.e., number and percentage of subjects with an event). When summarizing the number and percentage of subjects with an event, subjects with multiple occurrences of the same AE or a continuing AE will be counted once. Only the maximum severity level will be presented in the severity summaries, and the strongest relationship level will be presented in the relationship summaries.

In addition, a listing containing individual subject AE data for TEAEs leading to treatment discontinuation, serious adverse events (SAEs), and deaths will be provided separately. All AEs, including pretreatment AEs, will be presented in an individual subject data listing.

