12.3.4.2 Clinical Laboratory Assessments

For treatment-emergent laboratory measurements, the raw values and change-from-baseline values of the continuous hematology and chemistry results will be summarized in SI units by treatment group and visit.

The number and percentage of subjects with at least 1 laboratory event outside threshold criteria for the event during the TE period will be summarized overall and by treatment group, including a shift of the event from baseline to post-baseline. The threshold criteria will be provided in the SAP.

A listing of subjects with elevated LFT results during the TE period will be presented based on any of the following: AST $>3 \times$ ULN, ALT $>3 \times$ ULN, GGT $>3 \times$ ULN, ALP $>3 \times$ ULN, or total bilirubin $>2 \times$ ULN. For each subject in the listing, LFT assessments at all time points will be included (scheduled and unscheduled).

Results of the urine/serum pregnancy test will be listed in individual subject data listings only.

In addition, a listing containing individual subject hematology and chemistry values outside the normal reference ranges will be provided. This listing will include data from both scheduled and unscheduled visits.

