7.2 Sample Size and Power

Study 116 Part A enrolled subjects from Study 113 Part B and Study 115. No formal sample size calculations were performed. Approximately 56 subjects from Study 113 Part B and approximately 65 subjects from Study 115 were potentially eligible for enrollment.

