10.3 Safety Analysis

The primary objective of Study 116 Part A is to evaluate the long-term safety and tolerability of TEZ/IVA. The overall safety profile of study drug will be assessed in terms of the following safety and tolerability endpoints:

- Treatment-emergent adverse events (TEAEs)
- Clinical laboratory values
- Standard 12-lead ECGs
- Vital signs
- Pulse oximetry
- Ophthalmologic examination

Analysis of AEs will be based on events that occur during the TE period of the Part A, for all subjects in the Safety Set. Pooled AE data from Study 113 Part B and Study 115 (only those who received TEZ/IVA) will be displayed side-by-side with AE data from Study 116 Part A. When displayed side-by-side with parent study results, exposure-adjusted rates will be provided.

Other safety analyses will be based on data from the TE period for all subjects in the Safety Set; and will be presented overall. The Safety Set will be used for all listings unless otherwise specified.

Baseline value will be used to calculate change from baseline for continuous safety endpoints.

Only descriptive summaries will be presented, and no statistical testing is planned.

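### SAP 10.3 does not split the safety summaries by prior TEZ/IVA exposure, so first-time starters are averaged with subjects already on drug for about 8 or 24 weeks

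*SAP*

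**What the plan says.** **Protocol.** For AEs, section 12.3.4.1 states: "AE summary tables will be presented for TEAEs only, overall and by treatment group". For continuous laboratory results, section 12.3.4.2 says they "will be summarized in SI units by treatment group and visit". Sections 12.3.4.3 and 12.3.4.4 ask for the same breakdown of ECG and vital-sign data. The protocol does not say what the treatment groups of Study 116 are.

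**SAP.** Section 10.3 bases the AE analysis on all subjects in the Safety Set. It then covers the remaining safety data in one sentence: "Other safety analyses will be based on data from the TE period for all subjects in the Safety Set; and will be presented overall". Sections 10.3.1 to 10.3.5 contain no split by parent study or by prior treatment. For AEs only, a comparison with the parent studies is added: "Pooled AE data from Study 113 Part B and Study 115 (only those who received TEZ/IVA) will be displayed side-by-side", with exposure-adjusted rates.

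**Clocks.** Under SAP 9.1 the treatment-emergent (TE) period starts at the first Study 116 dose for everyone. Under SAP 10.1 the safety baseline precedes the first TEZ/IVA dose, whichever study that dose was taken in. SAP 10.1 and 10.2.2 both allow for subjects whose first TEZ/IVA dose falls in Study 116.

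**The concern.** The Safety Set holds three kinds of subject: those from Study 113B, those randomised to TEZ/IVA in Study 115, and those randomised in Study 115 to something else, who begin TEZ/IVA at Study 116 Day 1. For the last group the TE period covers the start of treatment. For the other two it begins after about 24 or 8 weeks on drug. One overall column therefore mixes initiation with continued exposure and describes neither cleanly.

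The side-by-side AE table does not separate them. Its parent column is limited to TEZ/IVA recipients, so the starters' first weeks on drug fall in the Study 116 column, next to the later experience of everyone else. Exposure adjustment divides by time; it does not separate early events from late ones.

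Time to onset of the events of special interest (SAP 10.3.1.4) is also not split. SAP 10.1 sets Day 1 at the first Study 116 dose. If onset is counted from there, it measures time since starting the drug only for the starters.

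**Working it through.** **Inputs from the documents**
- Eligible subjects: Protocol 12.1, "Approximately 56 subjects from Study 113B and approximately 65 subjects from Study 115 are potentially eligible for enrollment"; SAP 7.2 agrees. The protocol synopsis gives the total: "Up to approximately 121 subjects are potentially eligible for enrollment". Check: 56 + 65 = 121, which reproduces. This is a count of eligible subjects, not of subjects enrolled.
- No power calculation exists to reproduce: "No formal sample size calculations have been performed".
- Time in the parent study at entry: Week 24 visit (113B) or Week 8 visit (115), from Protocol 8.1.
- Starters exist (SAP 10.1, 10.2.2), and the efficacy models exclude Study 115 subjects not randomised to TEZ/IVA (SAP 10.4.2.1 to 10.4.2.4). Neither their number nor the Study 115 allocation ratio is given.

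**Assumptions.** A share f of the 65 Study 115 subjects are starters, with f from 0.20 to 0.50. All 113B subjects received TEZ/IVA; this is inferred from the efficacy restriction being applied to Study 115 only. Any gap between parent study and Day 1 is ignored, hence 'about' 8 and 24 weeks.

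**Step 1: exposure behind one visit label** (weeks on drug = Study 116 week + parent-study weeks)

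| Study 116 visit | Starters | 115 TEZ/IVA | 113B |
|---|---|---|---|
| Week 12 | 12 | 12 + 8 = 20 | 12 + 24 = 36 |
| Week 24 | 24 | 32 | 48 |
| Week 96 | 96 | 104 | 120 |

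The longest exposure is 3 times the shortest at Week 12 (36/12) but only 1.25 times at Week 96 (120/96). The mixing matters most early.

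**Step 2: share of a starter-only excess that remains visible.** With s starters among N subjects,

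pooled risk = [s × p(starter) + (N − s) × p(continuing)] / N,

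so (pooled risk − p(continuing)) / (p(starter) − p(continuing)) = s/N, whatever the two risks are.

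| f (assumed) | s | s/121: AE and TE-period threshold tables | s/65: Day 15 and Week 4 rows |
|---|---|---|---|
| 0.20 | 13 | 10.7% | 20.0% |
| 0.25 | 16 | 13.2% | 24.6% |
| 0.33 | 22 | 18.2% | 33.8% |
| 0.50 | 32 | 26.4% | 49.2% |

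The last column uses 65 because only Study 115 subjects have Day 15 and Week 4 visits (Protocol 9.1.1). Those rows cover vital signs and pulse oximetry at both visits, and chemistry and haematology at Day 15 only.

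**Step 3: illustration with assumed risks** of 15% in starters and 3% in continuing subjects:
- s = 13: (13 × 0.15 + 108 × 0.03)/121 = 5.19/121 = 4.3%
- s = 32: (32 × 0.15 + 89 × 0.03)/121 = 7.47/121 = 6.2%

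A split table would show 15% against 3%.

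**The case against.** The strongest reply is that the protocol's grouping has no defined content. The study is not randomised (Protocol 9.2) and has one treatment arm (SAP 7.3). Read literally, overall and by treatment group may coincide, and the wording may be template text. A reader might infer that the SAP removed a grouping the protocol had specified by parent-study treatment. The documents do not support that: the nearest use of the term, for the Study 115 TEZ/IVA arm, is in the efficacy text of Protocol 12.3.3.2. What stands is that the SAP drops the protocol's term without defining it or explaining its removal.

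Second, a reader might infer that early effects are hidden altogether. They are not:
- The parent AE column shows the first 8 or 24 weeks of those who started there, which on the assumed range is 121 − 32 = 89 to 121 − 13 = 108 of those eligible.
- SAP 10.3.1.1 and 10.3.2 list serious events, deaths, discontinuations, interruptions and elevated liver tests by subject.
- The Day 15 and Week 4 rows contain no 113B subjects.

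All of this stands as mitigation. None of it summarises the starters on their own, and the parent column serves AEs only.

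Third, a split cannot show first-weeks effects on ECG, lipids or vitamins, because their first scheduled assessment after Day 1 is Week 24 (Protocol Table 3-1). This is correct, and it limits the remedy.

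Fourth, the columns would be small. One event in 13 is 7.7%, and 0 of 13 is compatible with a true risk up to 1 − 0.025^(1/13) = 25% (exact two-sided 95%); for 0 of 32 the limit is 11%. This is also correct, but the output is descriptive and no testing is planned.

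**Conclusion.** The point holds as a gap in presentation on the primary endpoint. The Study 116 safety summaries combine three exposure histories, the protocol's treatment-group term was dropped without explanation, and neither the side-by-side AE table nor the unsplit time-to-onset summary separates initiation from continued treatment.

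The exposure mixing (about 12, 20 and 36 weeks at Week 12) follows from the documents, apart from the small assumptions stated. The dilution is conditional: 11% to 26% of a starter-only excess visible overall, and 20% to 49% at Day 15 and Week 4, if starters are 20% to 50% of the Study 115 subjects and all 121 eligible subjects enrol. It should not be quoted as a measured property of this trial. The 15% and 3% risks are illustrative only.

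The SAP already identifies these subjects. Its descriptive efficacy tables show Study 115 subjects randomised to TEZ/IVA alongside Study 115 overall, and demographics, medical history, medications and compliance are shown by parent study.

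**What to change.** In SAP 10.3:

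1. Define the safety grouping as prior TEZ/IVA exposure: 113B; 115 TEZ/IVA; 115 not TEZ/IVA. State that this is how the protocol's treatment-group wording is applied, or record the departure and the reason.
2. Present the AE, events-of-special-interest (including time to onset), laboratory and liver-test threshold, and vital-sign summaries by these groups and overall. State the time origin used for time to onset.
3. Give new starters their own column in the side-by-side AE table.
4. ECG, lipid and vitamin tables may be split in the same way so that each column has a consistent exposure time, but this should not be described as a way to detect first-weeks effects.

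The cost is extra columns in planned tables, built from identifiers the SAP already uses. No test is added, so multiplicity does not arise. The downside is small groups with imprecise percentages; counts and denominators should be shown with every percentage.

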10.3.1 Adverse Events

For analysis purposes, AEs will be classified as pretreatment adverse events (AEs), TEAEs, or post-treatment AEs, defined as follows:

- **Pretreatment AE** any AE that started before the first dose of study drug.
- **TEAE:** any AE that worsened (either in severity or seriousness) or that was newly developed during the TE period.

- **Post-treatment AE:** any AE that worsened (either in severity or seriousness) or that was newly developed after the TE period.

For AEs with completely missing or partially missing start dates, if there is no clear evidence that the AEs started before or after the first dose of study drug during the respective TE period, the AEs will be classified as TEAEs.

Details for imputing missing or partial AE start/end dates are defined in [Appendix E](#).

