8.1 Inclusion Criteria

1. Subject's legally appointed and authorized representative will sign and date an informed consent form (ICF) and the subject will sign an assent form (if applicable).
2. Willing and able to comply with scheduled visits, treatment plan, study restrictions, laboratory tests, contraceptive guidelines, and other study procedures.
3. Completed the Week 24 Visit in Study 113B or the Week 8 Visit in Study 115.

Added guidance:

- Subjects who had a study drug interruption at the last scheduled visit of Study 113B or Study 115, subjects who required study drug interruption that was to be continued or initiated at Day 1 in Study 116, or subjects who resumed study drug in the parent study after a study drug interruption due to elevated transaminases, but who did not complete at least 4 weeks of rechallenge with study drug (due to the timing of the rechallenge versus the time remaining in the parent study), must receive approval from the Vertex medical monitor.

Note: Subjects who permanently discontinue study drug treatment during the parent study, including at the last visit of the Treatment Period, are not eligible.

4. Did not withdraw consent from the parent study.
5. Subjects must have a genotype listed in [Appendix 1: CFTR Mutations](#). Note: Additional mutations may be evaluated and updates to the list of eligible mutations will be communicated to investigative sites through a memorandum. If TEZ/IVA receives marketing authorization for additional mutations in any country/region for patients ≥ 12 years old, a memorandum will be sent to investigative sites in that country/region and the newly approved mutations will also be eligible.
6. Willing to remain on a stable CF medication regimen through the Safety Follow-up Visit.

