11.4.3 Liver Function Test Parameters

Liver function testing (alanine transaminase [ALT], aspartate transaminase [AST], gamma-glutamyl transferase [GGT], alkaline phosphatase [ALP], direct bilirubin, and total bilirubin) must be performed as noted in [Table 3-1](#) for serum chemistry while subjects are receiving study drug treatment and at the Safety Follow-up Visit. These blood samples should be processed and shipped immediately per the Laboratory Manual.

Subjects with new treatment-emergent ALT or AST elevations of $>3 \times$ upper limit of normal (ULN) and clinical symptoms must be followed closely, including repeat confirmatory testing performed by the central laboratory within 48 to 72 hours of the initial finding and subsequent close monitoring of ALT and AST levels, as clinically indicated. In addition, if ALT or AST is $>5 \times$ ULN, repeat follow-up levels must be obtained within 7 ± 2 days.

If a subject cannot return to the site for confirmatory liver function testing, a local laboratory may be used. Elevations in LFTs at the local laboratory must be reported immediately to the medical monitor, and the subject must have the tests repeated and sent to the central laboratory as soon as possible (ideally within 48 to 72 hours).

Study Drug Interruption:

Study drug administration **must be interrupted** immediately (before confirmatory testing), and the medical monitor must be notified, if any of the following criteria is met:

- ALT or AST $>8 \times$ ULN
- ALT or AST $>5 \times$ ULN for more than 2 weeks
- ALT or AST $>3 \times$ ULN, in association with total bilirubin $>2 \times$ ULN and/or clinical jaundice

A thorough investigation of potential causes should be conducted and the subject should be followed closely for clinical progression.

If no convincing alternative etiology (e.g., acetaminophen use, viral hepatitis, or alcohol ingestion) for the elevated transaminases is identified, regardless of whether ALT or AST levels have improved, study drug treatment must be permanently discontinued if repeat testing within 48 to 72 hours confirms the initial elevation. Subjects in whom treatment is discontinued for elevated transaminases should have their transaminases monitored closely until levels normalize or return to baseline.

Resumption of Study Drug:

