9.1 Study 116 Analysis Periods

The Safety analysis period is defined as the **treatment emergent (TE) Period**. The safety analysis period begins at the first dose of study drug in Study 116 Part A and ends 28 days after the last dose of study drug in Study 116 Part A, or at the date of Study 116 Part A participation completion, whichever occurs first.

The safety analyses will be performed on the Safety Set over the Safety Analysis Period, unless otherwise specified.

Safety and tolerability will be assessed by clinical review of all relevant parameters including AEs, Physical Exams, ophthalmologic examinations, clinical laboratory values, vital signs, ECG measurements, and pulse oximetry.

Only descriptive summaries will be presented, and no statistical testing is planned.

Completion of study participation in Study 116 Part A is defined as one of the following:

- For subjects who complete Study 116 Part A and do not roll over to Part B: The Safety Follow-up Visit
- For subjects who complete Study 116 Part A and roll over to Part B or transition to Commercial Drug: The Week 96 Visit
- For subjects who prematurely discontinue study drug treatment but do not withdraw consent in Study 116 Part A: the latest of early treatment termination (ETT) Visit, or Safety Follow-up Visit (if applicable)
- For subjects who withdraw consent in Study 116 Part A: date of withdrawal of consent
- For subjects who are lost to follow-up in Study 116 Part A: the date of last contact

The efficacy analysis period begins at the first dose of study drug in Study 116 Part A and ends at the last study visit at which efficacy data are collected in Study 116 Part A as described in the visit window in the Appendix A. The efficacy analysis will be performed on all subjects in the FAS by parent study for the efficacy analysis period, unless specified otherwise.

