10.2.3 Medical History

Medical history (referenced to the start of parent study) will be coded by using the Medical Dictionary for Regulatory Activities (MedDRA) system organ class (SOC) and preferred term (PT), and will be summarized based on the FAS and displayed by 115/116 FAS, and 113B/116 FAS, and overall.

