10.3.1.1 Overview of TEAEs

An overview table of TEAEs will be provided with the following categories:

- Number of TEAEs (total number of TEAEs)
- Subjects with any TEAEs
- Subjects with TEAEs by strongest relationship
- Subjects with TEAEs by maximum severity
- Subjects with related TEAEs
- Subjects with Grade 3/4 TEAEs
- Subjects with serious TEAEs
- Subjects with related serious TEAEs (possibly related, related or missing)
- Subjects with TEAEs leading to treatment discontinuation
- Subjects with TEAEs leading to treatment interruption
- Subjects with TEAEs leading to death

The frequency counts and percentages will be presented for the above overview table. Exposure adjusted event rates may also be provided.

In addition, listings containing individual subject adverse event data for TEAEs leading to treatment discontinuation, treatment interruptions, SAEs and all deaths will be provided separately, with a flag indicating the TEAE status for SAEs and deaths.

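### An AE that began on parent-study TEZ/IVA, does not worsen, and leads to stopping or interrupting drug in Part A is left out of the AE discontinuation, interruption and special-interest summaries

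*SAP*

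**What the plan says.** SAP 9.1 fixes the start of the treatment-emergent (TE) period: "The safety analysis period begins at the first dose of study drug in Study 116 Part A". SAP 10.3 limits the AE analysis to it: "Analysis of AEs will be based on events that occur during the TE period of the Part A". SAP 10.3.1 defines a pretreatment AE as "any AE that started before the first dose of study drug" and a TEAE as "any AE that worsened (either in severity or seriousness) or that was newly developed during the TE period". What was done with study drug plays no part in either definition.

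The overview table (SAP 10.3.1.1) and the SOC/PT tables (10.3.1.2) cover discontinuation and interruption for TEAEs only. The special-interest summaries (10.3.1.4) are limited to treatment-emergent events. On listings, 10.3.1.1 says that "listings containing individual subject adverse event data for TEAEs leading to treatment discontinuation, treatment interruptions, SAEs and all deaths will be provided separately"; a flag for TEAE status is mentioned only for SAEs and deaths.

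Protocol 13.1.1.3 and 13.1.1.6 have the action taken with study drug recorded for each AE, including withdrawal and interruption.

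**The concern.** In a first-exposure trial a pretreatment AE arose off drug. Here that is often untrue. The Study 115 TEZ/IVA arm was on drug before Part A. So, by implication, were the Study 113B children, since the SAP restricts only Study 115 subjects to a TEZ/IVA arm. The SAP allows for this elsewhere: in 10.1 the safety baseline precedes the first TEZ/IVA dose, in whichever study it was taken. Laboratory change is thus measured from before drug, while an AE with onset on drug is filed as pretreatment. Medical history (SAP 10.2.3) is referenced to the start of the parent study, so it does not pick the event up.

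The primary endpoint is long-term safety and tolerability, and AEs that make a child stop or pause drug are central to tolerability. An event can force action without worsening. In Protocol 11.4.3, ALT or AST above 5 times "ULN for more than 2 weeks" is by itself a trigger for interruption, so persistence at one level is enough.

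**Working it through.** The plan states no figure to reproduce. The check applies the SAP's rules to cases and then asks which outputs admit them.

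**Classification under SAP 9.1 and 10.3.1**

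1. Onset on parent-study TEZ/IVA, ongoing, no worsening in Part A: pretreatment, not a TEAE.
2. Onset on parent-study TEZ/IVA, worsens in severity or seriousness in Part A: a TEAE.
3. New onset in Part A: a TEAE.

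Only case 1 is affected. The pretreatment definition does not say which study's drug it means, but the TE period is tied to Part A, so case 1 is not a TEAE on either reading.

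**Where case 1 appears if drug is stopped or interrupted after the first Part A dose**

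| Output | Event included? | AE tied to the Part A action? |
|---|---|---|
| TEAE discontinuation and interruption tables (SAP 10.3.1.1, 10.3.1.2) | No | No |
| Special-interest summaries (10.3.1.4) | No | No |
| Separate AE listings (10.3.1.1) | Discontinuation: no. Interruption: wording unclear | Only if admitted |
| Disposition table and listing (10.2.1) | Yes, if drug is stopped | Gives a reason; no AE term is specified |
| Exposure-based compliance (10.2.6) | Interruption days count | No cause shown |
| LFT threshold, shift and listing outputs (10.3.2) | Yes, if ALT or AST meets the criteria | No |
| Pooled parent-study AE data shown alongside (10.3) | Onset only | No |
| All-AE listing (Protocol 12.3.4.1) | Yes | Not in a count |

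**Example (assumed values).** ALT is 6 times ULN at the last parent-study visit, dosing continues into Part A, the value stays there for more than 2 weeks, and drug is interrupted. The child appears in the LFT outputs and the interrupted days lower compliance. The AE is absent from the interruption table and from the elevated-transaminase summary.

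**Size.** SAP 7.2 gives approximately 56 + 65 = 121 potentially eligible subjects. With k omitted children the shortfall is 100 × k/121 percentage points. The documents give no k, so the values below are assumed:

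- k = 1: 100 × 1/121 = 0.83
- k = 2: 100 × 2/121 = 1.65
- k = 3: 100 × 3/121 = 2.48
- k = 5: 100 × 5/121 = 4.13

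With fewer enrolled, each child weighs more. In SAP 10.2.1 and 10.3 the disposition categories and the AE tables both use the Safety Set, so a mismatch between them would not come from different denominators.

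**The case against.** The strongest reply is that most of the information is reported elsewhere. That stands. A discontinuation is in the disposition table and listing, interruption days enter compliance, and raised transaminases reach the LFT outputs whatever the AE's status, against a baseline that precedes TEZ/IVA. A serious event is in the flagged SAE listing, and the protocol lists all AEs, including pretreatment ones. A reader might infer that these events vanish, or that an interruption appears in no summary. The documents support neither. What the reply leaves open is the link: none of these outputs counts an AE together with the Part A action it caused, and an AE with no laboratory counterpart does not have the LFT outputs to fall back on.

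A second reply concerns how the case arises. Protocol 8.1 admits, with medical monitor approval, "subjects who required study drug interruption that was to be continued or initiated at Day 1 in Study 116", and also children with an unfinished rechallenge after raised transaminases. A reader might take these as ready examples. Mostly they are not. An interruption already in force before the first Part A dose is not a Part A action. Under Protocol 11.4.3, resumption follows a fall to 2 times ULN or less, or to baseline, so a later rise would ordinarily be new or worsened and hence a TEAE. (The parent studies' own resumption rules are not in these documents.) Children who stopped permanently in the parent study are ineligible. What remains is the child who rolls over while dosing with an ongoing AE that later prompts action at unchanged severity.

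Third, data capture is not visible. The documents do not say how a carried-over AE and a later action are entered in the Study 116 CRF. Protocol 13.1.1.2 treats an abnormal result as clinically significant when it leads to a dose change or discontinuation from the study, so a fresh Part A AE record is possible. This limits certainty about frequency, but it does not supply the missing rule.

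**Conclusion.** The point holds as a limited reporting gap. It concerns a non-serious AE that began on parent-study TEZ/IVA, is ongoing at the first Part A dose, does not worsen, and leads to withdrawal or interruption after that dose. The plan leaves such an AE out of the TEAE discontinuation and interruption tables and the special-interest summaries. AE-related discontinuations may then differ between the disposition and AE tables (assuming AE is among the recorded reasons), and the interruption has no AE summary row.

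The number affected is not given and is likely small; each omitted child is about 0.8 percentage points of 121. It would be tempting to treat every child already on TEZ/IVA, somewhere between 56 and 121, as affected. The documents do not support that: those totals are approximate counts of potentially eligible subjects, 121 includes Study 115 children not randomised to TEZ/IVA, and being on drug at rollover is not the same as having an ongoing AE that leads to action. Nor do the documents support any claim about the proportion of discontinuations missed.

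The TEAE definition is sound for counting onsets. The gap lies in using it to select AEs by what was done with drug. Because those tables serve the primary endpoint, the change should be made.

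**What to change.** In SAP 10.3.1.1 and 10.3.1.2, base the discontinuation and interruption rows, tables and listings on all AEs whose recorded action of drug withdrawn or drug interrupted was taken on or after the first Part A dose, regardless of onset. Show a TEAE flag and a flag for onset on parent-study TEZ/IVA. This also settles the unclear wording of the interruption listing.

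Leave the TEAE incidence tables and the exposure-adjusted rate numerators as they are, so that no onset is counted twice.

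In 10.3.1.4, add the number of subjects who enter Part A with an ongoing special-interest event that began on parent-study TEZ/IVA.

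The cost is SAP wording, one extra flag, and a check that carried-over AEs and their Part A action are captured in the Study 116 or integrated AE data. SAP 10.1 already plans to integrate the parent-study data. The discontinuation and interruption counts may become slightly less favourable. No clinical rule changes.
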